8.5 Method of Trial Vaccine Assignment

This trial is non-randomized. Eight vaccinated subjects in Groups 3 and 4 will receive two doses of CV7202 and the remaining 8 subjects in these groups will receive one dose of CV7202.

8.6 Blinding

This trial is open label.

8.7 Trial Vaccine and Supplies Accountability

It is the responsibility of the investigator to ensure that current and accurate records of trial supplies received, stored and dispensed at the site are maintained using appropriate forms according to applicable regulations and guidelines. The trial supplies must be stored under the recommended storage conditions, locked with restricted access (refer to the Handling Manual). Authorized personnel must dispense the vaccine at the trial site and in accordance with the protocol and applicable regulations and guidelines.

A dispensing log for CV7202 must be kept up-to-date at the trial site with the following information:

- a. Dates and quantities of CV7202 received from CureVac.
- b. Unique subject identifier.
- c. Date and quantity of trial vaccine dispensed to each subject.
- d. Initials of the person preparing the dose.
- e. Initials of the person administering the vaccine.

These accountability forms must be readily available for inspections and are open to regulatory inspection at any time.

8.8 Vaccine Compliance

The investigator will record all injections of trial vaccine (CV7202 and Rabipur®) given to the subject in the electronic eCRF.

8.9 Concomitant Therapy and Vaccines

Concomitant medication and vaccines must be recorded in the subject's eCRF.

If post-exposure vaccination for rabies is needed, the subject should be discontinued from receiving a further trial dose, but followed-up for safety assessments.

For additional information, refer to section 6.2.

8.10 Therapy leading to elimination

If a trial subject requires therapy listed as an exclusion criterion in section 6.2 and which cannot be delayed, discontinuation would be considered to ensure integrity of the trial data, following individual case review. Medications taken for prophylaxis (i.e. intended to prevent the onset of symptoms following vaccination) are not allowed.

8.11 Treatment after the End of the Trial

No post-trial care will be provided.

9 Trial Assessments and Procedures

The following sections describe the trial procedures and data to be collected. Additional trial-related information is provided in section 12, Appendix 1 to Appendix 17.

9.1 Adverse Events

Definitions and procedures for recording, evaluating, follow-up, and reporting of AEs are provided in Appendix 11. The intensity of AEs will be graded in the following manner:

| | | |
|-----------|-----------|---|
| Absent: | • Grade 0 | • No AE |
| Mild: | • Grade 1 | • An event that is easily tolerated by the subject, causing minimal discomfort and not interfering with everyday activities. |
| Moderate: | • Grade 2 | • An event that causes sufficient discomfort to interfere with normal everyday activities. |
| Severe: | • Grade 3 | • An event that prevents normal everyday activities. An AE that is assessed as severe should not be confused with a SAE. Severe is a category utilized for rating the intensity of an event; and both AEs and SAEs can be assessed as severe. |

Solicited AEs will be collected on the day of vaccination and the 7 subsequent days (Days 1-8) and the intensity grading will be applied (Table 9.1 and Table 9.2). By definition, all local solicited symptoms are considered related to vaccination.

Unsolicited AEs will be collected on the day of vaccination and the 28 subsequent days (Days 1-29).

Table 9.1 Intensity Grading for Solicited Local AEs (Days 1 to 8)

| AE | Grade | Definition |
|-------------------------|-------|--|
| Pain at injection site* | 0 | Absent |
| | 1 | Does not interfere with activity |
| | 2 | Interferes with activity and/or repeated use of non-narcotic pain reliever >24 hours |
| | 3 | Prevents daily activity and/or repeated use of narcotic pain reliever |
| Redness* | 0 | ≤2.5 cm |
| | 1 | 2.5 – 5 cm |
| | 2 | 5.1 – 10 cm |
| | 3 | >10 cm |
| Swelling* | 0 | ≤2.5 cm |
| | 1 | 2.5 – 5 cm and does not interfere with activity |
| | 2 | 5.1 – 10 cm or interferes with activity |
| | 3 | >10 cm or prevents daily activity |
| Itching | 0 | Absent |
| | 1 | Mild, no interference with normal activity |
| | 2 | Moderate, some interference with normal activity |
| | 3 | Significant, prevents normal activity |

*FDA toxicity grading scale [25].

Table 9.2 Intensity Grading* for Solicited Systemic AEs (Days 1 to 8)

| AE | Grade | Definition |
|---------------------|--------------|--|
| Fever | 0 | <38°C |
| | 1 | ≥38 – 38.4°C |
| | 2 | ≥38.5 – 38.9°C |
| | 3 | ≥39°C |
| Headache | 0 | Absent |
| | 1 | Mild, no interference with normal activity |
| | 2 | Moderate, some interference with normal activity and/or repeated use of non-narcotic pain reliever >24 hours |
| | 3 | Significant; any use of narcotic pain reliever and/or prevents daily activity |
| Fatigue | 0 | Absent |
| | 1 | Mild, no interference with normal activity |
| | 2 | Moderate, some interference with normal activity |
| | 3 | Significant, prevents normal activity |
| Chills | 0 | Absent |
| | 1 | Mild, no interference with normal activity |
| | 2 | Moderate, some interference with normal activity |
| | 3 | Severe, prevents normal activity |
| Myalgia | 0 | Absent |
| | 1 | Mild, no interference with normal activity |
| | 2 | Moderate, some interference with normal activity |
| | 3 | Significant, prevents normal activity |
| Arthralgia | 0 | Absent |
| | 1 | Mild, no interference with normal activity |
| | 2 | Moderate, some interference with normal activity |
| | 3 | Significant, prevents normal activity |
| Nausea/ Vomiting | 0 | Absent |
| | 1 | Mild, no interference with activity and/or 1 – 2 episodes/ 24 hours |
| | 2 | Moderate, some interference with activity and/or >2 episodes/ 24 hours |
| | 3 | Severe, prevents daily activity, requires outpatient i.v. hydration |
| Diarrhea | 0 | Absent |
| | 1 | 2 – 3 loose stools or <400 g/24 hours |
| | 2 | 4 – 5 stools or 400 – 800 g/24 hours |
| | 3 | 6 or more watery stools or >800 g/24 hours or requires outpatient IV hydration |

*FDA toxicity grading scale [25]; i.v. = Intravenous.

Laboratory data will be graded according with the FDA toxicity grading scale [25] and the Common Terminology Criteria for Adverse Events (CTCAE) Version 5.0 [26]. These guidelines however are dependent upon institutional normal parameters. Institutional normal reference ranges should be provided to demonstrate that they are appropriate.

AEs with a suspected immune mediated disease etiology will be considered AESIs. The list of AESI is provided in (Appendix 10).

Definitions and Procedures for Recording, Evaluating, Follow-up, and Reporting of AEs are provided in Appendix 11.

9.2 Safety Assessments

The following safety assessments apply to all subjects in Groups 1 to 4:

All vaccinations will be administered on an outpatient basis. All subjects will be monitored for 4 hours following administration of the trial IMP. Vital signs must be within normal ranges or have returned to pre-vaccination levels (pre-vaccination values \pm 15% or no clinically relevant deviation from pre-vaccination values) for the subject to be discharged.

All subjects will undergo a vaccination site reactogenicity assessment (injection site pain, redness, swelling and itching) at 1 hour post vaccination on the day of vaccination (Day 1, Day 8 [Rabipur® Dose 2] and Day 29 [Rabipur® and Groups 3a and 4a]) and 1 or 2 days after each vaccination (Day 2 or 3, Day 10 [Rabipur® Dose 2] and Day 30 or 31 [Rabipur® and Groups 3a and 4a]). Note that Days 3 and 31 were planned in the original protocol and only apply to subjects in Groups 1 and 2 who were already enrolled and vaccinated before this protocol amendment was issued. Days 2 and 30 apply to all other subjects. For those subjects, a phone call will be performed to collect safety information 2 days after each vaccination.

Local reactions at 1 hour post-vaccination will be assessed on an intensity scale of absent, mild, moderate and severe. The trial personnel will record these in the eCRF.

Diary cards will be distributed to all subjects and used to collect solicited local (injection site pain, redness, swelling and itching) and systemic (fever, nausea/vomiting, diarrhea, headache, fatigue, myalgia and arthralgia) AEs on the day of vaccination and the 7 subsequent days (Days 1 to 8, Day 8 to 15 [Rabipur® Dose 2] and Days 29 to 36). Local reactions and systemic events will be assessed on an intensity scale of absent, mild, moderate and severe. The diary card will be reviewed on Day 2 or 3, 8, 10, 15, 29, 30 or 31, 36, 43 and 57. In case of related grade 3 solicited or unsolicited AEs reported for more than 1 day on the diary card, the subject will be interrogated to establish the total duration of the AE and this information will be recorded in the medical file. Unsolicited AEs occurring on the day of vaccination (Day 1, Day 8 and Day 29) and for the following 28 days will be recorded by the subject on the diary card.

The occurrence of AEs (serious and non-serious) will be assessed by non-directive questioning of the subject at each visit. AEs volunteered by the subject during or between visits as subject diary card entries or detected through observation, physical examination, laboratory test, or other assessments during the entire trial, will be documented. Subjects will be instructed that they must immediately report any AEs with serious symptoms, subjective complaints or objective changes in their well-being to the investigator or the clinic personnel, regardless of the perceived relationship between the event and the test vaccine.

SAEs, MAAEs and AEs leading to trial or vaccine withdrawal will be collected up to 12 months after the last dose administration. After Visit 15 (Month 12), only SAEs and MAAEs that according to the investigator are considered to be related to study vaccination will be collected.

Intercurrent medical conditions and AESIs will be collected throughout the trial.

Clinical laboratory testing for safety evaluations are provided in Appendix 6. Definitions and procedures for recording, evaluating, follow-up and reporting of AEs are provided in Appendix 11.

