| Assess intercurrent medical conditions | 9.4.3-0 | | | | | | | | | | | | | | | | | | | | | | | | |
| Assess Concomitant Medications/Vaccinations | 9.4.2-0 | | | | | | | | | | | | | | | | | | | | | | | | |
| Assess AESIs | 9.4.3-0 | | | | | | | | | | | | | | | | | | | | | | | | |
| Assess SAEs related to study vaccination ^m | 9.4.3-0 | | | | | | | | | | | | | | | | | | | | | | | | |
| Assess MAAEs related to study vaccination ^m | 9.4.3-0 | | | | | | | | | | | | | | | | | | | | | | | | |
| Safety Lab ⁱ (~9 ml) | 9.4.2-9.4.5, 9.4.8-9.4.11, 9.4.14-9.4.17 | | | | | | | | | | | | | | | | | | | | | | | | |
| TSH, Thyroid antibodies, ANA (~3 ml) [§] | 9.5.2 | | | | | | | | | | | | | | | | | | | | | | | | |
| Immunogenicity | | | | | | | | | | | | | | | | | | | | | | | | | |
| VNTs (serum) ^l (~18ml) | 9.4.3, 9.4.5, 9.4.8, 9.4.9, 9.4.11-0 | | | | | | | | | | | | | | | | | | | | | | | | |
| IgM/ IgG/ IgA ELISA (serum) ^l (~6 ml) | 9.4.3, 9.4.5, 9.4.8, 9.4.9, 9.4.11-0 | | | | | | | | | | | | | | | | | | | | | | | | |
| Cellular immune response and leukocyte phenotyping (PBMCs) ^{i, l} (~40-60 ml) | 9.4.3, 9.4.5, 9.4.11, 9.4.15-9.4.17 | | | | | | | | | | | | | | | | | | | | | | | | |
| Cytokine assessment (serum) ^{i, l} (~6 ml) | 9.4.3-9.4.5, 9.4.9-9.4.11 | | | | | | | | | | | | | | | | | | | | | | | | |
| Transcriptome profiling (PBMCs) ^{i, l} (~10ml) | 9.4.3, 9.4.4, 9.4.9, 9.4.10 | | | | | | | | | | | | | | | | | | | | | | | | |
| Immune receptor sequencing (PAXgene DNA) ⁱ (~5ml) | 9.4.3, 9.4.5, 9.4.9, 9.4.11, 9.4.14-9.4.17 | | | | | | | | | | | | | | | | | | | | | | | | |
| Maximum total blood volume (ml) | Table 9.3 | 3 | 11 | 120 | 25 | 0 | 94 | 0 | 33 | 60 | 25 | 0 | 94 | 24 | 38 | 78 | 78 | 78 | 78 | 24 | 24 | 24 | 24 | | |
| Trial end | | | | | | | | | | | | | | | | | | | | | | | | | |

Notes:

M6 corresponds to Day 181 (1-dose groups) and Day 209 [2-dose groups and Group 1 (Rabipur®)].

M12 corresponds to Day 365 (1-dose groups) and Day 393 [2-dose groups and Group 1 (Rabipur®)].

M18 corresponds to Day 547 (all groups).

M24 corresponds to Day 729 (all groups).

Vaccinations planned at Visit 3 (Dose 1 for Groups 1 to 4), Visit 5 (Dose 2 Rabipur® for Group 1), Visit 8 (Dose 2 for Groups 3a and 4a, Dose 3 Rabipur® for Group 1).

* The pre-screening and screening visits can be performed on the same day.

** The Day 2 and Day 30 visits should be performed at around 24 +/- 2 hours after the vaccination.

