^d Second vaccination of CV7202 will be given only to 8 subjects in Groups 3 and 4 (i.e. Groups 3a and 4a).

^e Physical examination and vital signs must be performed/analyzed by a qualified healthcare professional.

^f Vital signs to be checked: body temperature, pulse, blood pressure. Vital signs will be measured pre- and post-vaccination prior to discharge. Subjects will be observed for 4 hours following each vaccination; vital signs must be within normal or clinically non-relevant abnormal ranges or have returned to pre-vaccination values for the subject to be discharged from the phase I Unit.

^g All vaccinated subjects will undergo vaccination site reactogenicity assessment at 1 hour post-vaccination on the day of vaccination (Day 1, Day 8 and Day 29) and 1 or 2 days after each vaccination (Day 2 or 3, Day 10 and Day 30 or 31). Note that Days 3 and 31 were planned in the original protocol and only apply to subjects in Groups 1 and 2 who were already enrolled and vaccinated before this protocol amendment was issued. Local reactions (injection site pain, redness, swelling and itching) will be assessed on an intensity scale of absent, mild, moderate and severe.

^h Solicited and unsolicited AE diaries. Solicited AEs occurring on the day of vaccination (Day 1, Day 8 and Day 29) and for the following 7 days will be recorded by the subject on the diary card. The diary card will be reviewed on Day 2 or 3, 8, 10, 15, 29, 30 or 31, 36, 43 and 57. Unsolicited AEs occurring on the day of vaccination (Day 1, Day 8 and Day 29) and for the following 28 days will be recorded by the subject on the diary card.

ⁱ The VNT serum sample is intended as the baseline value and must be taken before vaccination on Day 1 and Day 29.

^j Hematology (complete blood count, including differential and platelets), biochemistry.

^k Coagulation (activated partial thromboplastin time [aPTT]) and prothrombin time/international normalized ratio (INR) will be performed at the following time points: Screening, Day 1, Day 2 or 3 and Day 30 or 31.

^l In the first 5 subjects in Group 2 and all subjects in Groups 3 and 4. 60 ml for the baseline (Day 1) time point, 40 ml for subsequent blood draws.

^m At each study visit/contact preceding Month 18, SAE and MAAEs considered as related to study vaccination were collected as part of all SAEs and MAAEs.

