9.4.3 Visit 3 (Vaccination Dose 1 CV7202 or Dose 1 Rabipur®, Day 1)

The following procedures will be performed during Visit 3:

- Review of eligibility criteria (sections 6.1 and 6.2).
- Review of criteria for vaccine delay (section 6.3).
- Urine pregnancy test for female subjects of childbearing potential, unless the serum pregnancy test was performed less than 3 days before.
- Physical examination (including weight and general condition) and vital signs check (body temperature, pulse, blood pressure).
- Blood draw for:
 - Safety laboratory (~9 ml).
 - Immunogenicity – VNTs (~18 ml), IgM/IgG/IgA (~6 ml), PBMCs* for CMI (~60 ml), cytokine assessment (~6 ml at pre-vaccination and ~6 ml at 4 hours post-vaccination [CV7202 groups only]), transcriptome profiling (~10 ml at pre-vaccination [CV7202 groups only]), immune receptor sequencing (~5 ml).
- * PBMCs will be taken for a subset of the first 5 subjects in Group 2 and all subjects in Groups 3 and 4.
- **Vaccination (Dose 1 CV7202 or Dose 1 Rabipur®).**
- Post-injection vaccination site reactogenicity assessment after 1 hour for all subjects. Note that all subjects need to remain at the site for 4 hours after vaccination for safety monitoring. Vital signs will be then re-checked and have to be within normal ranges or have returned to pre-vaccination levels for the subject to be discharged.
- Subjects will be issued with diary cards to record solicited AEs occurring on the day of vaccination and the following 7 days. Unsolicited AEs occurring on the day of vaccination and for the following 28 days will also be recorded by the subject on the diary card. Subjects will be instructed on how to complete the diaries.
- Safety assessments (solicited AEs, unsolicited AEs, SAEs, intercurrent medical conditions, AEs leading to trial or vaccine withdrawal, AESIs and MAAEs, concomitant medications and vaccinations).

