9.4.6 Visit 5 (Vaccination Dose 2 Rabipur®, Day 8)

The following procedures will be performed during Visit 5:

Group 1 only: Vaccination (Dose 2 Rabipur®):

- Review of criteria for vaccine delay (section 6.3).
- Urine pregnancy test for female subjects of childbearing potential.
- **Vaccination (Dose 2 Rabipur®).**
- Post-injection vaccination site reactogenicity assessment after 1 hour and then subjects will be discharged if the vital signs are within normal ranges or have returned to pre-vaccination levels.
- Diary collection for solicited AEs occurring up to Day 8 (Dose 1 Rabipur®).
- Subjects will be issued with diary cards to record solicited AEs occurring on the day of vaccination (Dose 2 Rabipur®) and the following 7 days. Unsolicited AEs occurring on the day of vaccination up to Day 29 will also be recorded by the subject on the diary card. Subjects will be instructed on how to complete the diaries.

Groups 2-4 only:

- Diary review for solicited AEs occurring up to Day 8 (Dose 1 CV7202).
- Diary card returned to the subjects for collection of unsolicited AEs up to Day 29 (Dose 1 CV7202).

All subjects:

- Physical examination (including weight and general condition) and vital signs check (body temperature, pulse, blood pressure).
- Blood draw for:
 - Safety laboratory (~9 ml).
 - Immunogenicity – VNTs (~18 ml), IgM/IgG/IgA (~6 ml), PBMCs* for CMI (~40 ml), cytokine assessment (~6 ml [CV7202 groups only]), transcriptome profiling (~10 ml [CV7202 groups only]), immune receptor sequencing (~5 ml).
* PBMCs will be taken for a subset of the first 5 subjects in Group 2 and all subjects in Groups 1, 3 and 4.
- Safety assessments (solicited AEs, unsolicited AEs, SAEs, intercurrent medical conditions, AEs leading to trial or vaccine withdrawal, AESIs and MAAEs, concomitant medications and vaccinations).

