9.4.9 Visit 8 (Vaccination Dose 2 CV7202* or Dose 3 Rabipur®, Day 29)

The following procedures will be performed during Visit 8:

- Review of criteria for vaccine delay (for Groups 1, 3a and 4a section 6.3).
- Urine pregnancy test for female subjects of childbearing potential.
- Physical examination (including weight and general condition) and vital signs check (body temperature, pulse, blood pressure).
- Blood draw for:
 - Safety laboratory (~9 ml).
 - Immunogenicity – VNTs (~18 ml), IgM/IgG/IgA (~6 ml) and immune receptor sequencing (~5 ml) in all subjects; cytokine assessment (~6 ml at pre-vaccination and ~6 ml at 4 hours post-vaccination [CV7202 groups only]) and transcriptome profiling (~10 ml at pre-vaccination [CV7202 groups only]) in subjects from Groups 3a and 4a who received a second dose of CV7202.

* The second dose will be administered to 8 subjects of each group (Groups 3a to 4a).

- **Vaccination (Dose 2 CV7202 or Dose 3 Rabipur®).**
- Post-injection vaccination site reactogenicity assessment after 1 hour for all subjects who received a vaccine. Note that all subjects need to remain at the site for 4 hours after vaccination for safety monitoring. Vital signs will be then re-checked and have to be within normal ranges or have returned to pre-vaccination levels for the subject to be discharged.
- Diary review and collection for unsolicited AEs occurring up to Day 29 (Dose 1 CV7202 and Rabipur®) and up to Day 36 (Dose 2 Rabipur®).
- Subjects will be issued with diary cards to record solicited AEs occurring on the day of vaccination with Dose 2 CV7202 or Dose 3 Rabipur® and the following 7 days. Unsolicited AEs occurring on the day of vaccination and for the following 28 days will also be recorded by the subject on the diary card.
- Safety assessments (solicited AEs, unsolicited AEs, SAEs, intercurrent medical conditions, AEs leading to trial or vaccine withdrawal, AESIs and MAAEs, concomitant medications and vaccinations).

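### The ±15% discharge margin in Protocol 9.2 does not exempt body temperature, where it reaches about 41.4 to 42.6 °C

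*Protocol*

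**What the plan says.** The discharge check after vaccination is described in five places in the Protocol.

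- **Section 9.2.** Vital signs must be normal or back at pre-vaccination levels. A parenthesis explains the latter as pre-vaccination values ± "15% or no clinically relevant deviation from pre-vaccination values) for the subject to be discharged". The section does not say which vital signs the percentage covers.
- **Table 2.1, note f.** It defines the set: "Vital signs to be checked: body temperature, pulse, blood pressure". It then gives a discharge rule without a percentage: "vital signs must be within normal or clinically non-relevant abnormal ranges or have returned to pre-vaccination values for the subject to be discharged".
- **Section 9.4.3 (Day 1).** Re-checked vital signs "have to be within normal ranges or have returned to pre-vaccination levels for the subject to be discharged".
- **Section 9.4.6 (Day 8, Rabipur).** After the one-hour site assessment, "subjects will be discharged if the vital signs are within normal ranges or have returned to pre-vaccination levels".
- **Section 9.4.9 (Day 29).** "Vital signs will be then re-checked and have to be within normal ranges or have returned to pre-vaccination levels".

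The three visit sections list temperature among the vital signs and give no margin.

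Two other places deal with temperature, both in absolute degrees. Table 9.2 grades fever from 38 °C (grade 1), 38.5 °C (grade 2) and 39 °C (grade 3, with no upper bound). Section 6.3 delays vaccination when temperature is above 38.0 °C.

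**The concern.** A 15% margin is workable for pulse and blood pressure. It is not workable for temperature in °C, where a few per cent separates a normal reading from a high fever. Because the percentage part of the parenthesis is sufficient alone, a clearly febrile subject can be recorded as back at the pre-vaccination level with no judgement about clinical relevance.

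Fever is a foreseeable event here. Section 5.8.1 lists it as an expected side effect of CV7202, and the exceptions to the stopping rules in 5.1.2 name transient grade 3 fever. What is at stake is the written standard for sending home recipients of a first-in-human product. The analysis is not affected.

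**Working it through.** The Protocol states only the ±15% rule and no resulting temperature, so there is no plan figure to reproduce. The check is what the rule implies for temperature.

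**Inputs**
- Margin: ±15% of the pre-vaccination value (9.2).
- Fever thresholds: 38.0, 38.5 and 39.0 °C (Table 9.2).
- Pre-vaccination temperature *b*: not given in the documents. Assumed 36.0, 36.5 and 37.0 °C, with 35.5 and 38.0 °C as a wider range. Section 6.3 delays vaccination above 38.0 °C, which supports the upper end.

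**Step 1. Limits of the margin:** lower = 0.85 × *b*, upper = 1.15 × *b*.

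| *b* (°C) | 0.15 × *b* | Lower | Upper |
|---|---|---|---|
| 36.0 | 5.40 | 30.60 | 41.40 |
| 36.5 | 5.475 | 31.03 | 41.98 |
| 37.0 | 5.55 | 31.45 | 42.55 |

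At 35.5 °C the upper limit is 40.8 °C; at 38.0 °C it is 43.7 °C.

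**Step 2. Rise needed to reach each fever grade:** 100 × (threshold / *b* − 1).

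| *b* (°C) | Grade 1 (38.0) | Grade 2 (38.5) | Grade 3 (39.0) |
|---|---|---|---|
| 36.0 | 5.6% | 6.9% | 8.3% |
| 36.5 | 4.1% | 5.5% | 6.8% |
| 37.0 | 2.7% | 4.1% | 5.4% |

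Every entry is well below 15%.

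**Step 3. Dependence on the assumed baseline.** A threshold lies inside the margin when *b* exceeds threshold / 1.15: 38.0 / 1.15 = 33.04, 38.5 / 1.15 = 33.48 and 39.0 / 1.15 = 33.91 °C. All three grades therefore begin inside the margin for any baseline above about 33.9 °C, so the conclusion does not turn on the assumed values.

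**Step 4. One subject under both texts.** Take 36.5 °C before vaccination and 40.0 °C at the check. The rise is 100 × (40.0 / 36.5 − 1) = 9.6%, so the percentage part of 9.2 is met. Under note f read alone, 40.0 °C is neither normal nor back at the starting value, so the subject could leave only if the reading were judged clinically non-relevant.

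**The case against.** **The authors plainly meant pulse and blood pressure.** Probably so, but the text does not say it. A mandatory discharge rule should state its scope, and doing so takes one phrase.

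**Section 9.2 and note f do not conflict.** A reader might infer that the Protocol sets two rival standards, with note f the stricter. The documents do not establish that. Section 9.2 can be read as the definition behind the shorter wording in the visit sections, and plausibly behind note f as well. Note f is also looser in one respect: it admits clinically non-relevant abnormal ranges, where the opening condition of 9.2 admits only normal ranges. The judgement-based allowances nearly coincide, so the difference lies in the percentage alone. This part of the objection stands. It does not rescue the margin, since reading 9.2 as the definition carries the same temperature limit into the other sections.

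**Some fevers still fail.** Correct. Grade 3 is open-ended, so readings above the upper limit are excluded. The accurate statement is that each grade begins inside the margin.

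**Safeguards make it academic.** Largely true. Note e of Table 2.1 requires that "Physical examination and vital signs must be performed/analyzed by a qualified healthcare professional". CV7202 recipients are observed for 4 hours. Under the amended schedule, "The Day 2 and Day 30 visits should be performed at around 24 +/- 2 hours after the vaccination", and a phone call follows on Day 3 (Day 31 after a second CV7202 dose). The diary captures fever. SAP 6.4 also records that 53 subjects, including 16 + 16 + 10 = 42 CV7202 recipients, had been vaccinated and observed to Day 57 by the second interim analysis, so dosing was complete. All this lowers the severity but does not make the stated limit sensible.

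**A firm ceiling of below 38.0 °C would be cleaner.** It is tempting, but section 6.3 permits vaccination at exactly 38.0 °C, so such a subject with an unchanged temperature could not be discharged. Whether every low-grade fever should keep an outpatient on site is also debatable, because the Protocol treats fever as expected and manageable symptomatically (5.8.1, 5.8.5).

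**Conclusion.** The point holds as a minor drafting correction. As written, the ±15% in 9.2 covers body temperature and sets an upper limit of 41.4 to 42.6 °C at assumed baselines of 36.0 to 37.0 °C. Readings in all three fever grades, up to that limit, satisfy this part of the rule. The exact limit rests on the assumed baselines; the conclusion needs only a baseline above 33.9 °C.

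It should not be inferred that febrile subjects were sent home or that any result is affected. The documents give no onset time for fever and no discharge data, and no endpoint or stopping rule uses this threshold. With dosing complete, the value of the change lies in a correct written standard and in any later reuse of the wording.

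**What to change.** In 9.2, restrict ±15% to pulse and blood pressure. For body temperature use note f's standard: within the normal or a clinically non-relevant abnormal range, or back at the pre-vaccination value, with no percentage margin. Use the same wording in 9.4.3, 9.4.6 and 9.4.9. Note f already carries this standard. A subject vaccinated at exactly 38.0 °C whose temperature is unchanged can still be discharged.

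The cost is one sentence in 9.2 and matching text in three visit sections, made through the procedure in Appendix 8 and able to travel with another amendment. No new measurement is needed, because temperature is already among the vital signs checked before discharge. The SAP needs no change.
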